The RA will read the consent to screen script on REDCap. Potential participants are free to stop at any time – remind them that all procedures are completely voluntary. [name] and/or someone from the Lab Management team will always be onsite to help answer questions.

Participants will then be given an eligibility screener via tablet with either [name] or a trained research assistant available to answer any questions. The screener will first assess for age, prior homelessness, and cognitive competence. The screener then screens for PTSD using the PTSD Checklist for DSM-5 (PCL-5) for *the worst event in their life*. We will assess PTSD to their most recent event (in the past year) during the baseline and follow-up assessments. The standard PCL-5 initially starts with the identification of the presence of exposure to a DSM-5 traumatic event and then assesses whether it involved actual or threatened death, serious injury or sexual violence. The RA may need to prompt the potential participant with examples to keep them on track and to ensure that the participant is responding to an actual DSM-5 traumatic event. The next 20 items on the PCL-5 assess all four B-E PTSD criterion (re-experiencing, avoidance, negative thoughts or cognitions, hyperarousal), assessed on a Likert-type scale 0 "not at all", 1 "a little bit", 2 "moderately", 3 "quite a bit", 4 "extremely". Subthreshold PTSD will be defined as endorsing "moderately" or more to at least 2 B-E criteria; probable-PTSD will be measured by meeting criteria A-G for PTSD.

Data collection method: All data will be collected via encrypted tablets will be programmed by the Research Director from the School of Nursing and responses will be automatically, electronically scored. Data is not stored on the tablets. It is automatically transferred to the All participants who complete the screener will receive \$3.

Subsection 2.5 - Phase II Eligibility Criteria

Inclusion Criteria:

- 1) Homeless women (N=134; 67 in each group)
 - a. Women over 18 years of age
 - b. Able to speak English
 - c. Homeless in the last 6 months: a homeless person is defined as anyone who spent the previous night in a public or private shelter, or on the street.
 - d. Lifetime exposure to trauma as defined by the Diagnostic and Statistical Manual for Mental Disorders, 5th Edition (DSM-5).
 - e. Likely subthreshold or threshold PTSD, as measured by the PCL-5.

Exclusion Criteria:

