Saliva samples will be immediately placed in the on-site freezer or cooler and be taken to IISBR or to [name] research lab for storage. Saliva samples will be transferred to IISBR within 36 hours to be frozen at -80°C until assayed. After the second and final collection, participants will be offered snacks and a drink and be debriefed using an IRB-approved script (see below).

Debriefing script:

Thanks so much for your participation. I know that might have been difficult for you to recall this event. I want to thank you and let you know that we think your participation in this task will help other women who have experienced adversity. While feeling a little distressed might be expected, we want to make sure you are not experiencing a lot of distress. Right now are you are experiencing a lot of distress?

If yes, ask if they want you to get a site staff from Prototypes/Serenity House AND contact the Principal Investigator, [name] [name] immediately AND provide [name] contact information to them).

If no, thank them for their time and remind them if anything comes up they can call the Principal Investigator, [name] [name] and/or talk to any of the Prototypes/Serenity House site staff. (Provide [name] contact information to them).

Provide water and snacks at this time and pay close attention to any noticeable changes in mood until they are released to the care of the Prototypes/Serenity House site staff. Immediately inform [name] AND Prototypes/Serenity House site staff of any potential issues.

Subsection 2.11 - Phase II Biospecimen Analysis

Urine Sample: The 5-panel FDA-approved urine test cup screens for metabolites of the following drugs of abuse at the established cut-off levels and is used for qualitative purposes: Amphetamines (1000 ng/mL), Cocaine (300 ng/mL), Methamphetamines/ MDMA (500 ng/mL), Opiates (2000 ng/mL), and THC (50 ng/mL). Urine sample validity checks will be provided by temperature and adulterant monitoring strips built into the test cup. Participants whose urine does not pass validity checks will be counted as positive for drugs. Results will be coded qualitatively (above or below threshold). All positive results will be interpreted as positive, regardless of self-report.

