APPENDIX IV: Citations for Study Measures

Primary Outcome:

PTSD Checklist for DSM-5 (PCL-5; Weathers, Litz, Keane, Palmieri, Marx, & Schnurr, 2013). Responses will be scored continuously and according to diagnostic criteria as implemented in previous research.(143) The PCL-5 initially starts with the identification of the presence of exposure to a DSM-V traumatic event (i.e., "Briefly identify the worst event (if you feel comfortable doing so)") and then assesses whether it involved actual or threatened death, serious injury or sexual violence; whether the person directly experienced it (through direct exposure, witness to the event, occurred to a close friend or family member, or exposed as part of job). There are then twenty-items that assess all four B-E criterion (re-experiencing, avoidance, negative thoughts or cognitions, hyperarousal), assessed on a Likert-type scale 0 "not at all", 1 "a little bit", 2 "moderately", 3 "quite a bit", 4 "extremely".

Secondary outcomes:

Substance use:

Self-report drug use: Texas Christian University (TCU) Screen at Baseline and 6-month follow up. Yes/No to each drug will be assessed for use vs dependency. The total score ranges from 0 - 9; higher scores (> 3) correspond to the DSM drug dependence diagnosis. This will be assessed at baseline, immediately following 9th/final intervention session, and 6-month follow-u (Institute of Behavioral Research, 2017).

Objective drug use assessment: A 5-panel FDA-approved urine test cup will be used in this study. The test cup screens for metabolites of the following drugs of abuse at the established cut-off levels and is used for qualitative purposes: Amphetamines (1000 ng/mL), Cocaine (300 ng/mL), Methamphetamines/ MDMA (500 ng/mL), Opiates (2000 ng/mL), and THC (50 ng/mL). Urine sample validity checks will be provided by temperature and adulterant monitoring strips built into the test cup. Participants whose urine does not pass validity checks will be counted as positive for drugs. Results will be coded qualitatively (above or below threshold). All positive results will be interpreted as positive, regardless of self-report.

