All analyses were conducted using STATA 18. First, descriptive statistics were calculated for the total sample. Next, a series of multilevel models were conducted for each primary and secondary outcomes using a multilevel, random-intercept mixed. Participants were entered as random effects to nest observations within participants, allowing for correlations within each individual over time. Group assignment (i.e., MBSR vs. HP Control), time (i.e., T1, T2, and T3), and group-by-time interactions were entered as fixed effects. Site was also included as a fixed-effect, given the low number (i.e., two) of sites¹. Covariates were screened for inclusion in bivariate analyses and included if statistically significant and theoretically meaningful. An independent covariance pattern was specified as our final models were random-intercept (nested within participant) only². Results are presented using restricted maximum likelihood for optimal control of Type 1 error³. An intention-to-treat analysis was conducted, where every participant was included in the final analyses, regardless of whether they completed all of the sessions.

Bibliography

- 2. Weise RE. *Modeling Longitudinal Data*. 1st ed. Springer; 2005.
- 3. Luke SG. Evaluating significance in linear mixed-effects models in R. *Behav Res Methods*. 2017;49(4):1494-1502. doi:10.3758/s13428-016-0809-y

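### The SAP gives every outcome the same REML random-intercept model and makes no provision for the binary urine drug result, or for PTSD diagnosis if it is analysed; for urine, model-based standard errors can be materially wrong

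*Combined protocol and SAP*

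**What the plan says.** The Statistical Analysis Plan is one paragraph with one modelling rule: "a series of multilevel models were conducted for each primary and secondary outcomes using a multilevel, random-intercept mixed". The sentence stops there, without naming a distribution or link. The fixed part is then given: "Group assignment (i.e., MBSR vs. HP Control), time (i.e., T1, T2, and T3), and group-by-time interactions were entered as fixed effects", with site as a further fixed effect. On the variance side, "An independent covariance pattern was specified as our final models were random-intercept (nested within participant) only". On estimation, "Results are presented using restricted maximum likelihood for optimal control of Type 1 error", supported by a reference titled "Evaluating significance in linear mixed-effects models in R". Robust standard errors are not mentioned, and no outcome is exempted.

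Appendix IV lists the outcomes. Under the secondary heading for substance use it includes the five-panel urine cup, for which "Results will be coded qualitatively (above or below threshold"); Subsection 2.11 repeats this coding. Subsection 2.2 has urine collected at baseline, after the ninth session and at 6 months. For the primary outcome, the PCL-5, Appendix IV says "Responses will be scored continuously and according to diagnostic criteria as implemented in previous research". Table 4 schedules a PTSD diagnosis at the screen and at both follow-ups, and its footnote b adds it to the baseline questionnaire. The SAP does not say which PCL-5 scoring is modelled.

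**The concern.** REML, together with a reference on linear mixed models, points to a Gaussian model with the same residual variance at every visit. A yes/no outcome does not have that property: its variance is p(1 − p) and moves with the positive rate p. If the rate differs between visits, the model spreads an average variance over all of them. A group-by-time contrast that involves low-rate visits then gets too large a standard error, and one that involves a high-rate visit gets too small a one.

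This matters mainly for urine. Women enrol while living in residential drug treatment, and Subsection 2.14 expects some to have moved to sober living or elsewhere by follow-up, so a rate that is low early and higher later is plausible. The urine test is the objective measure within a named secondary outcome, and a false-positive rate well above 5% at 6 months would bear directly on a claim about drug use.

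**Working it through.** **The plan's own arithmetic.** The only design figures are the participant flow in Subsection 2.16: 448 × 0.30 = 134.4; 134 × 0.90 = 120.6; 120 × 0.80 = 96.0. The stated 134, 120 and 96 are reproduced, with the 20% loss applied to the 120. With equal arms, the numbers per arm are 67, 60 and 48.

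**Assumptions.** The documents give no urine-positive rate, so the rates below are assumed. Within-woman correlation is set to zero, the rates are equal in the two arms (the null), and the test is two-sided at 5%.

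**Formulas.** With per-arm numbers m_t and v_t = p_t(1 − p_t):

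- pooled residual variance s² = Σ m_t v_t / Σ m_t
- model variance of the T_k-versus-T1 group contrast ∝ s²(1/m_1 + 1/m_k)
- true variance ∝ v_1/m_1 + v_k/m_k
- SE ratio R = √(model variance / true variance)
- true error = 2·P(Z > 1.96 R)

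**Rates 5%, 10%, 35%.** v = 0.0475, 0.0900, 0.2275, and s² = (67 × 0.0475 + 60 × 0.0900 + 48 × 0.2275)/175 = 0.1114.

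- T2: model 0.1114 × (1/67 + 1/60) = 0.00352; true 0.0475/67 + 0.0900/60 = 0.00221. R = √1.594 = 1.26, error 1.3%.
- T3: model 0.1114 × (1/67 + 1/48) = 0.00399; true 0.0475/67 + 0.2275/48 = 0.00545. R = √0.731 = 0.86, error 9.4%.

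**Other assumed rates, same formulas.**

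| Rates T1/T2/T3 | R at T2 | error at T2 | R at T3 | error at T3 |
|---|---|---|---|---|
| 5/10/35% | 1.26 | 1.3% | 0.86 | 9.4% |
| 10/15/40% | 1.15 | 2.5% | 0.90 | 7.7% |
| 5/5/25% | 1.34 | 0.8% | 0.82 | 11.0% |
| 10/10/10% | 1.00 | 5.0% | 1.00 | 5.0% |

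**Simulation check.** The design was simulated with 67 women per arm, three visits, 10% and then a further 20% dropout at random, and binary data from a random-intercept logistic model with intercept SD 0.7, 1.5 or 2.5 on the logit scale (assumed). The linear REML model with group, time, group-by-time and site was fitted in 4,000 runs per scenario. Ranges are over the three SDs, and over T2 and T3 unless one visit is named.

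| Scenario | SE ratio | null rejection |
|---|---|---|
| Diagnosis 70/50/50%, or flat 50% | 0.98–1.02 | 4.7–6.0% |
| Diagnosis 95/50/50% | 0.95–1.05 | 4.2–6.5% |
| Urine flat at 10% | 0.97–1.00 | 5.0–6.3% |
| Urine 30/5/25%, T3 | 0.88–0.96 | 6.1–8.1% |
| Urine 5/5/25%, T2 | 1.33–1.39 | 0.7–1.0% |
| Urine 5/5/25%, T3 | 0.81 | 11.2–11.4% |

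The 5/5/25% rows agree with the formula. Bias in the risk-difference contrasts was at most 0.004 throughout, so the fault lies in the standard errors and not in the point estimates.

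**Alternatives.** Participant-clustered robust standard errors on the same linear model gave null rejection of 4.9–6.2% in all these scenarios. A mixed logistic model with a Wald test (SD 1.5, 600 runs) was close to nominal at moderate rates (4.3–5.2% for flat 50% and 70/50/50%). At 5/5/25% it rejected only 1.0% at T2 and 2.5% at T3, with near-separated or non-finite estimates in 14.5% and 5.7% of runs.

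**The case against.** The SAP never names the urine result or the diagnosis as a modelled outcome, and its key sentence is incomplete. Several passages describe urine as a check on self-report, and the primary analysis may well use the continuous PCL-5 score. This stands in part: a reader might infer that both binary variables were in fact fitted as Gaussian, and the documents do not establish that. They do establish a rule for each secondary outcome and a list of secondary outcomes that includes a binary one. If urine was left out of the modelling, the SAP should say so.

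A reader might also infer that the standard errors of any binary outcome under this plan are wrong. The working does not support that: at moderate or stable rates the error is near nominal, and the opposite-direction pattern at T2 and T3 comes from the assumed rise in the rate. Nor is a mixed logistic model required. In the sparse setting that motivates the concern it was conservative and unstable, while robust standard errors on the existing model restored about 5%. Fitted proportions outside 0–1 are a minor worry, because group, time and their interaction are saturated and only the site term is additive.

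Finally, Subsection 2.4 says "probable-PTSD will be measured by meeting criteria A-G for PTSD", while the twenty items are described as covering B to E. One might conclude that the diagnosis cannot be scored. That goes too far: Appendix IV defers scoring to previous research, and the REDCap instruments are not shown. It is a definition to supply, separate from the choice of model.

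**Conclusion.** The point holds in limited form. The plan states a single rule that does not suit a listed secondary outcome, and it gives no alternative. The continuous PCL-5 score is untouched, and for PTSD diagnosis the practical error is small at the rates examined. For urine the size depends on rates the documents do not give. It is negligible if the rate is stable near 10%. If positives are rare early and commoner at 6 months, the T2 test is too conservative (true error about 0.7–2.5%) and the T3 test too liberal (about 7.7–11.4%) over the rising patterns examined.

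These figures assume the planned 134/120/96, dropout at random, equal arms and the stated rates. The formula results also assume zero within-woman correlation; the simulation relaxes that. Neither accounts for clustering by class within site and cohort, which is a separate matter.

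**What to change.** Add a few sentences to the SAP:

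- State which PCL-5 scoring is primary, and restrict the REML linear model with model-based standard errors to continuous outcomes.
- List the binary outcomes: the urine result, and PTSD diagnosis if it is analysed, with its scoring rule written out.
- For these, pre-specify one analysis with valid variances. Either keep the same linear model with participant-clustered robust standard errors and report risk differences, or use a logistic model (GEE or mixed) with marginal risk differences and a stated fallback for sparse or separated data.

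The cost is those sentences and a changed Stata option or command. The main downside falls on the logistic route, which can be conservative or fail to give usable estimates when positives are rare. GEE logistic was not simulated here.

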Arm: The different groups of the intervention. In this study, Arm 1 is the health promotion attention control and Arm 2 is the MBSR. Participants at a given site are assigned to one Arm or the other, by cohort).

Cohort: The group of people that are doing the interventions at the same time.

Cortisol: The body's main stress hormone, triggered by the adrenal glands. Cortisol is a glucocorticoid and is released in the body about 20 minutes after a stressor. The immediate stress response hormones (adrenaline and epinephrine) are released within seconds or minutes; if the brain continues to perceive something as stressful, then cortisol is released.

C-Reactive Protein (CRP): This is a protein made in the liver. CRP tends to increase when there is inflammation occurring in the body, (Lindqvist et al., 2014, 2017) induced by proinflammatory cytokines in the liver (Eklund, 2009). These heightened inflammatory responses can lead to health impairments including atherosclerosis (Wong et al., 2012) and cardiovascular disease (Coughlin, 2011) compounding health disparities in disadvantaged populations; CRP, in particular, has been linked with obesity (Visser et al., 2011) metabolic syndrome (Ridker et al., 2003) and CVD.(Ridker et al., 1998) Thus CRP can be used as marker for general inflammation and risk for inflammatory-related problems.

Other acronyms used in this protocol:

IISBR - Institute for Interdisciplinary Salivary Bioscience Research - https://iisbr.uci.edu/

- IISBR is a shared resource and scientific hub; researchers can gain practical experience/knowledge in salivary bioscience through the training programs (e.g., Spit

Camp). IISBR also provides the storage and analyses of the salivary samples collected in this study.

SECTION 1B. INTRODUCTION TO PTSD AND MBSR

Subsection 1B.1 - PTSD Basics

PTSD Diagnosis

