In Phase II, we will assess the potential benefit of MBSR to reduce PTSD (primary outcomes) and secondary outcomes (e.g., depression, SUD, CRP, cortisol reactivity), among 130 eligible homeless women who exhibit likely subthreshold or threshold PTSD living at one of two residential drug treatment facilities. MBSR will be compared to an attention-control group (Health Promotion Wellness Classes; HP). There originally intended to be five cohorts of women, each with 12-15 women (total of 24-30 women per cohort). However, due to COVID-19 adjustments have been made in terms of the class size and randomization procedure. At each cohort, sites will be randomized to receive either the MBSR or the HP. Although sites will alternate between MBSR and HP by cohort, each participant will receive either the MBSR or the HP. Randomization will occur using RedCAP. The women participate in either MBSR or HP for 9 weeks. Psychosocial data will be collected at baseline, immediately following final intervention session, and at 6-month follow-up via tablet questionnaires. After psychosocial data collection, a stress task (Trauma Imagery Task) will be conducted at each time point, with saliva collected both before and after the task to assay cortisol and CRP. This proposal will improve on the methodological rigor of prior research on MBIs for PTSD in disadvantaged populations by using: randomization procedures that account for cross-contamination; blind evaluators; longitudinal follow-up; an attention control group equal to the MBI intervention in both contact visits and hours; increased demographic diversity; comprehensive lifetime trauma assessment; and inclusion of objective indices of stress responses to accurately evaluate the effectiveness of MBIs in treating trauma-related symptoms.

Confidentiality and Ethical Issues

All program staff must follow confidentiality and ethical procedures throughout this program to ensure that everybody is treated with respect and dignity.

1. Communication with study participants must remain confidential. To maintain confidentiality for participants, any personal information provided, such as participants' name, age, etc., will

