- c. Tablets will be programmed by the Research Director from the School of Nursing and responses will be automatically, electronically scored. All participants who complete the screener will receive \$3.
 - i. Note: those who complete the screener must complete the consent to screen, but are not assigned a participant ID at this time as they have not completed the **Informed Consent**. As such it is imperative that accurate information be obtained with respect to the individual's name as that will be used to link it to their subsequent data.

- 2. Group Assignment and Intervention Procedure (may chance due to evolving circumstances due to COVID-19)
 - a. Prior to recruitment, the Residential Treatment Sites (RTS; Pomona and Escondido) will be randomized to receive the MBI or serve as the attention-control (HP); recruitment and research procedures (MBI or attention-control) will occur at both sites simultaneously. Women will live at sites prior to recruitment.
 - b. Informed consent there are TWO versions of the Informed Consent documents. One is for the MBSR course: the other is for the HP course. Women will complete ONE of the Informed Consent forms, depending on which group they are in. It is imperative that the correct form is filled out and uploaded onto REDCap.
 - c. Baseline questionnaire administered:
 - i. After informed consent, participants will complete a baseline questionnaire. In addition to the traumas indicated in the PCL-5, participants will report lifetime history of trauma (including whether events occurred in adulthood, childhood, or both).
 - ii. Questionnaire data will be collected via tablet and transferred to RedCap.
 - iii. Participants will provide a urine sample for a drug test to validate self-report. Then participants will complete the brief stress (Trauma task providing saliva samples both before and after the task.
 - d. Locator guide: this is a critical part of maintaining contact with our participants. However, they may not be inclined to provide all the information on the first or second meeting. PLEASE TAKE THE PICTURE AT THE TIME OF ADMINISTERING **INFORMED CONSENT.** The rest of the locator guide can be filled out over the course of the study. Given issues with COVID-19, we will start completing the Locator Guide after session 2 or 3. Please see PI or Lab Management Team for further guidance.
 - e. Intervention

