KEY = Urine collected for drug screen = Saliva collected immediately before & 20 min post trauma imagery task ^a Measures: lifetime trauma exposure (+ occurrence in adulthood, childhood or both); demographics ^b Updated adversity history (traumatic & stressful events, including incarceration), PTSD dx ^c Depression, self-report substance use, perceived stress, mindfulness, fidelity/ adherence to program, quality of life													

Subsection 2.4 - Phase II Recruitment & Screening

The study was designed so that recruitment at Pomona would be paced to match that at the Escondido site so that all procedures across sites happen in tandem, thus avoiding history effects; recruitment data will be evaluated weekly to inform pacing. Site staff at Prototypes will assist with participant recruitment, informing Prototypes residents of the opportunity during formal announcements during programing. Recruitment flyers will also be posted around the RTS. RAs will help recruit women and conduct the initial screening in a private room after obtaining informed consent; progress will be monitored closely by [name] the Lab Management team. Modifications will be made to allow for the study to continue during the COVID-19 pandemic to ensure safety of Ras, site staff, and participants.

Ideally, recruitment will be staggered according to cohorts and paced equally across sites. In total, five cohorts of women will be recruited. Each will have approximately 26- 28 women in each group/site (n=13-14 MBSR; n=13-14 attention control); recruitment proceeds for one month, the intervention runs for approximately 2 months (9 weeks), then there is one month break. *However, this schedule may vary due to COVID-19 restrictions, limitations, and other feasibility issues*.

[name] will explain the study during an initial meeting with potential participants and answer any questions. Then women will be screened for eligibility. Prior to obtaining any data, the women will provide a "consent to screen". This is because we need to obtain data from the women to determine if they are eligible, but they are not officially enrolled as human subjects. By providing their "consent to screen", we are obtaining verbal consent/permission to ask them questions. Their data will not be used by the research team if they are not eligible.

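### Arms are assigned to whole site-by-cohort classes, but the SAP model has no class level, so class-specific differences in change make its group-by-time standard errors too small

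*Combined protocol and SAP*

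**What the plan says.** Three places in the protocol describe allocation, and none randomises individual women.

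- Basic Definitions, under Arm: "Participants at a given site are assigned to one Arm or the other, by cohort".
- Subsection 2.1: "At each cohort, sites will be randomized to receive either the MBSR or the HP", and then "Although sites will alternate between MBSR and HP by cohort, each participant will receive either the MBSR or the HP".
- Subsection 2.2, item 2a: "Prior to recruitment, the Residential Treatment Sites (RTS; Pomona and Escondido) will be randomized to receive the MBI" or act as the control.

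Subsection 2.4 plans five cohorts with 13–14 women per arm in each, taught at two sites running in parallel. That is 10 classes. The layout is not firm. Subsection 2.1 says that "due to COVID-19 adjustments have been made in terms of the class size and randomization procedure", item 2 of Subsection 2.2 warns that group assignment may change, and the Year 3 calendar shows cohorts 6–7.

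The Statistical Analysis Plan fits group, time, group-by-time and site as fixed effects. Of the random part it says: "Participants were entered as random effects to nest observations within participants, allowing for correlations within each individual over time". It adds that the final models were random-intercept only. It mentions no class or cohort term, no cluster-robust variance and no class-based degrees of freedom.

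**The concern.** All women in a class share one arm, one instructor, one group and one period. If some classes improve more than others for reasons unrelated to arm, the number of independent units behind the arm comparison is nearer the number of classes than the number of women. The protocol makes such variation plausible: Subsection 2.13 grants that being in a group could itself help, and Subsections 2.12 and 2.19 allow delivery to flex to the group.

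The SAP model treats women as independent given their own intercept. At stake is the false-positive rate of the primary PCL-5 test and of every secondary group-by-time test. No class ICC is reported and no check for class variation is planned, so a reader cannot judge how far a moderately significant result may rest on one or two unusual classes.

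**Working it through.** **Plan's own figures (Subsection 2.16).** 448 × 0.30 = 134.4 enrolled; 134 × 0.90 = 120.6 at T2; 120 × 0.80 = 96 at T3. These reproduce the stated 134 / 120 / 96. With 10 classes there are 120/10 = 12 women per class at T2 and 96/10 = 9.6 at T3.

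**Assumed, because the documents are silent.** Two-sided 5% test; ICC = class share of the variance of T1–T2 change, at 0.02 / 0.05 / 0.10.

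**What cancels.** Group-by-time is a difference between arms in change from T1. A class effect constant over time drops out of every woman's change. A cohort effect on change that is common to both concurrent classes drops out of the arm difference when one class is in each arm. Only class-specific change remains.

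**Closed form at T2.** Set total variance of change to 1. If a share *s* of the class variance is common to the cohort, the true variance of the arm contrast relative to what the model assumes is about

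V = (1 − ICC) + 12 × ICC × (1 − s),

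and the rejection rate is 2 × [1 − Φ(1.96/√V)].

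| Share common to cohort | V at ICC 0.02 / 0.05 / 0.10 | T2 rejection of a true null |
|---|---|---|
| s = 0 | 1.22 / 1.55 / 2.10 | 7.6 / 11.5 / 17.6% |
| s = 0.5 | 1.10 / 1.25 / 1.50 | 6.2 / 8.0 / 11.0% |
| s = 1 | 0.98 / 0.95 / 0.90 | 4.8 / 4.4 / 3.9% |

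**Simulation of the SAP model** (REML, normal reference, within-person correlation 0.5, dropout 134/120/96, alternating sites, s = 0):

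- T2 at ICC 0 / 0.02 / 0.05 / 0.10: 5.4 / 8.2 / 12.9 / 18.8%.
- T2 and T3 with class differences constant over time (ICC 0.05): both 5.2%.
- T3 at ICC 0.02 / 0.05 / 0.10, by how much of the T2 difference persists: all, 7.3 / 11.1 / 16.9%; half, 5.8 / 6.5 / 8.6%; none, 5.0 / 4.4 / 4.4%.
- Joint 2-df group-by-time test, full persistence: 8.0 / 12.1 / 18.2%.
- T2 with 12 or 14 classes: 7.0–7.4 / 10.0–10.8 / 15.3–17.1%.

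**Second simulation**, with class variance scaled to total variance and correlation 0.6: T2 7.8–9.2 / 13.1–14.5 / about 20%. A variance of 0.05 is here 0.05/(0.05 + 0.80) = 0.059 of the variance of change, which partly explains the higher figures. A class difference of variance 0.05 that first appears at T3 gave T3 11.6% and T2 4.8%.

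**Effective sample, s = 0.** T2: 120/(1 + 11 × ICC) = 98 / 77 / 57. T3, under full persistence: 96/(1 + 8.6 × ICC) = 82 / 67 / 52.

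**Candidate remedies at 10 classes.**

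- Class-mean change, site fixed, 10 − 3 = 7 df (critical t 2.36): about 5% without shared cohort change, about 2–3% with it.
- The same with cohort also fixed, 10 − 1 − 1 − 1 − 4 = 3 df (critical t 3.18): about 5% either way.
- SAP model plus class and class-by-time random effects, no cohort terms, at ICC 0 / 0.02 / 0.05 / 0.10: a normal reference gave 4.9 / 6.7 / 7.9 / 10.8%, and t on 7 df gave 1.6 / 3.0 / 3.9 / 5.5%.

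**The case against.** The best defence is the design. Each cohort is meant to have one class per arm, with the sites run in parallel to avoid history effects (Subsection 2.4). Period effects, including those of COVID-19, would then largely cancel. This stands: the 8 / 12–13 / 18–19% figures are upper values for the assumed ICC, and with full sharing there is no inflation. It does not remove variation due to the instructor, the group or the site at that moment, and no document shows that such variation is absent.

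Several stronger readings are tempting but unsupported.

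- *The SAP test is known to over-reject.* Only the missing class level is certain. Without an ICC the inflation is conditional, and a very small p-value could survive it.
- *T3 is at risk only if a T2 difference lasts.* A class difference first arising by T3 inflates T3 as well.
- *The estimate is biased.* Under random or alternating allocation, class-specific change affects the standard error, not the average estimate.
- *Arm and site are the same variable.* Item 2a of Subsection 2.2 could mean one randomisation. It could equally mean before each cohort's recruitment, which would agree with Subsection 2.1.
- *Cohorts 6–7 received MBSR only.* This rests on one cell of a calendar table that is visibly broken in extraction.

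**Conclusion.** The concern holds. The unit that received the arm is absent from the model that tests the arm. Neither the participant intercept nor the site main effect repairs this, because both are constant over time. REML, which the SAP cites for control of Type 1 error, does not repair it either.

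The size is conditional on the assumed ICC, a two-sided 5% test, 10 classes and the share of class variation common to a cohort. Across the range examined, T2 false rejection runs from about 5% (all shared) to 18–19% (ICC 0.10, none shared), and somewhat lower with 12–14 classes. Confidence is high in the omission and the direction of the error, and lower in the magnitude.

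**What to change.** 1. **Reconcile Subsection 2.1 with item 2a of Subsection 2.2**, and report how many classes each site ran in each arm. If sites were randomised once only, arm and site cannot be separated by any model, and the report should say so.
2. **Re-analyse the primary and secondary group-by-time tests with the class as the unit of inference.** Before re-running, name as the deciding analysis the SAP's all-participant model with class and class-by-time random effects, cohort-by-time terms and small-sample degrees of freedom. This keeps the intention-to-treat set. Check its null rejection rate by simulation for the actual layout, since Satterthwaite and Kenward–Roger degrees of freedom were not tested here.
3. **Sensitivity analysis:** class-mean change at T2 and T3 compared between arms with site and cohort fixed, on residual df (3 for five cohorts). Show the site-only version (7 df) beside it. These use only women with follow-up, so they drop about 134 − 120 = 14 women at T2 and 134 − 96 = 38 at T3.
4. **If cohorts 6–7 were MBSR only,** state that arm is partly confounded with calendar time and show results without them. With nine MBSR and five HP classes the mean cohort numbers are 41/9 = 4.56 and 15/5 = 3, so an assumed drift of 0.1 SD per cohort would bias the arm difference by 1.56 × 0.1 = 0.16 SD.

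**Cost.** No new data collection, since the SAP reports completed analyses. Each woman's cohort is needed and may have to be rebuilt from enrolment dates. Intervals widen and power falls. For an assumed effect of 0.5 SD of change at ICC 0.05, class-mean power is about 44–46% with site only and no cohort effect. It is about 31–32% with cohort adjusted, or with a shared cohort effect of variance 0.05. The SAP model has about 78% at ICC 0.
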